12.4 Subgroup Analysis

With the following exception, analyses of the primary and secondary efficacy endpoints (refer to Sections 12.1 and 12.2, respectively) and WI-NRS success will be repeated by subgroups (refer to Section 6.6) based on the multiple imputation data using the ITT population (primary and secondary endpoints) and the WI-NRS population (WI-NRS success). The exception is that the subgroup analyses by randomized vIGA-AD score and by actual baseline vIGA-AD score will not be performed for the secondary efficacy endpoint of vIGA-AD Success based on the vIGA-AD Moderate ITT population.

The following alternatives could be implemented if the odds ratio and/or proportion difference are not estimable:

1. An unstratified model can be used if odds ratios are not estimable due to over-stratification, i.e., too few events for the number of strata.
2. If the between-imputation variance of odds ratios and/or proportion difference is 0, i.e., the estimates are equal across all imputations, the estimates from any imputation will be reported.

Should a specific subgroup have less than 10 subjects across both treatment groups, no statistical inference will be performed. Forest plots of odds ratios and difference in percent of subgroup analysis for primary efficacy endpoint, secondary efficacy endpoints and WI-NRS success will also be provided.

 Innovaderm Research ■■■	STATISTICAL ANALYSIS PLAN, Version 1.0
Protocol Number: ARQ-151-315	Sponsor: Arcutis Biotherapeutics, Inc.

No subgroup analyses will be presented for the exploratory efficacy endpoint (refer to Section 2) except for WI-NRS success.

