6.2.1 Multiple Imputation

All subjects, regardless of completion status, will have available data assigned to the pre-specified analysis visit using the analysis windows defined in Section 5.4, including the last available data of subjects who prematurely withdraws from the study. To comply with the definition of the primary estimand (Section 12.1.1), for subjects who discontinue due to lack of efficacy or adverse event, efficacy data assigned to a pre-specified analysis visit will be removed from the source data used for the multiple imputation process if subject's last dose day falls within the analysis visit window or is prior to the start of the analysis visit window used to assign data to a pre-specified analysis visit. This procedure will ensure that the data collected on or after these specific intercurrent events are not used in the imputation process.

For the primary efficacy endpoint of vIGA-AD success at Week 4 and the secondary endpoint of vIGA-AD success at Week 4 among subjects with a 'Moderate' randomized vIGA-AD score, the primary analysis will impute missing values using a Predictive Mean Matching (PMM) sequential-regression multiple imputation model for the ITT population. This is a three-step process.

1. The first step is to understand the pattern of missingness. In order to perform the multiple imputation, a monotone missing pattern has to be achieved. For example, if there exist values for baseline and Week 4 visits, but missing values for the Week 1 or 2 visits, the Markov-Chain Monte-Carlo (MCMC) method will be used to impute the small amount of missing data that may be missing at the intermediate visits that is required to make the missing data pattern monotone before applying the multiple imputation algorithm. This method uses a non-informative Jeffreys prior to derive the posterior mode from the expectation-maximization (EM) algorithm as the starting values for the MCMC method. The MCMC method will use the seed 6457149. The vIGA-AD score will be treated as a continuous variable for this step and the model will include the vIGA-AD scores at baseline, Week 1, Week 2, and Week 4. To avoid values that could not be observed in practice, imputed values will be rounded to the nearest integer (Round=1 option in PROC MI) in the range of 0 to 4.

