To determine the number of multiply-imputed datasets to be created at this step, the proportion of datapoints with non-monotone pattern across all visits and subjects will first be derived as follows:

$$\frac{\text{number of non monotone visits accross all visits and subjects}}{\text{total number of expected visits accross all subjects}} * 100$$

 Innovaderm Research ■■■	STATISTICAL ANALYSIS PLAN, Version 1.0
Protocol Number: ARQ-151-315	Sponsor: Arcutis Biotherapeutics, Inc.

Then, the following table will be used:

Non-monotone Missing Data	Number of Imputed Datasets
$\leq 2\%$	1
$> 2\% \text{ to } \leq 5\%$	3
$> 5\%$	10

2. Once the monotone pattern is achieved, the next step is to implement the imputation algorithm. For this, the PMM regression method will be used. This method is particularly helpful if the normality assumption is violated. For subjects with complete data up to a particular visit, a PMM regression model will be fit that includes the outcome at that visit as the dependent variable and as independent variables, the treatment group, and vIGA-AD score outcomes at previous visits, using a seed of 482371. For other scales/questionnaires, the actual baseline vIGA score will also be included as an independent variable. This process will be repeated 25 times, resulting in a total of 25 to 250 complete analysis datasets, depending on the number of imputed monotone datasets that are required. The seed may be changed after unblinding in case of any issues with the imputation process, and it will be documented in the CSR if any change is required.
3. For each of the 25 to 250 completed datasets, the necessary derived variable will be computed as defined in Section 5.5 and analyzed using a CMH analysis, adjusted for the randomized vIGA-AD score for the primary efficacy endpoint. The treatment effect on the secondary efficacy endpoint dealing with vIGA-AD success in the vIGA-AD moderate ITT population will be assessed with an unstratified chi-square test. Results will be combined into one multiple imputation inference as follows:

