6.6 Examination of Subgroups

Subset analysis for the following subgroups will be performed for the primary, secondary and WI-NRS success efficacy endpoints:

- Gender (male vs. female),
- Race (White vs. Black or African American vs. Asian vs. other),
- Ethnicity (Hispanic vs. Non-Hispanic),
- Randomized vIGA-AD score (mild (2) vs. moderate (3)),
- Actual baseline vIGA-AD score (mild (2) vs. moderate (3)),

 Innovaderm Research ■■■	STATISTICAL ANALYSIS PLAN, Version 1.0
Protocol Number: ARQ-151-315	Sponsor: Arcutis Biotherapeutics, Inc.

- Baseline % BSA (<10% vs. \geq 10%),
- %BSA categories based on tertiles,
- Baseline EASI total score (\leq 7 vs $>$ 7),
- Baseline EASI total score based on tertiles
- Fitzpatrick skin type at Screening (Type I, II and III vs. Type IV, V, and VI),
- Prior inadequate response, intolerance, or contraindication to Topical Corticosteroids (yes vs. no),
- Facial Involvement (yes vs. no)

For subgroup based on tertiles, tertiles will be derived using pooled data from both treatment groups based on the ITT population.

Details on these analyses are described in Section [12.4](#).

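### SAP 12.4 takes subgroup effects from imputations that have no treatment-by-subgroup term and omit most subgroup factors, which draws differing effects slightly together

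*SAP*

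**What the plan says.** SAP 6.6 commits to subgroup results: "Subset analysis for the following subgroups will be performed for the primary, secondary and WI-NRS success efficacy endpoints". It lists 12 factors: sex, race, ethnicity, randomized and actual baseline vIGA-AD, two groupings of baseline BSA, two of baseline EASI, Fitzpatrick type, prior topical-steroid response and facial involvement. SAP 12.4 produces these results "based on the multiple imputation data using the ITT population (primary and secondary endpoints", with the WI-NRS population for WI-NRS success, and plots them as forest plots. It describes no imputation specific to a subgroup.

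The imputations come from SAP 6.2.1:

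- Step 1 fills non-monotone gaps by MCMC. For vIGA-AD, "the model will include the vIGA-AD scores at baseline, Week 1, Week 2, and Week 4"; treatment is not named.
- Step 2 is predictive mean matching and takes "as independent variables, the treatment group, and vIGA-AD score outcomes at previous visits".
- For other scales "the actual baseline vIGA score will also be included as an independent variable". EASI and average weekly WI-NRS follow a similar method.
- Neither step lists an interaction.

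Under SAP 5.5, children who stop for an adverse event or lack of efficacy count as non-successes at the affected visits. The non-responder and observed-data analyses are specified for whole analysis populations (SAP 12.1.3, 12.2 and 12.5). Nothing says that they are repeated by subgroup.

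**The concern.** A subgroup analysis asks whether the treatment effect differs between levels of a factor. An imputation model with one treatment coefficient and no interaction fills in missing outcomes largely as if it did not. The analysis then mixes observed outcomes, which can show a difference, with imputed outcomes, which mostly cannot. If effects truly differ, the forest plot is expected to look somewhat more uniform than the data warrant, and more so in levels with more imputed values. Such plots are read for consistency of effect. The plan offers no second set of subgroup results, with missing data handled differently, against which the pull could be seen.

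**Working it through.** **1. The plan's own figures.** The documents give no figure for dropout, subgroup effects or subgroup precision. Their power statement (SAP 5.1, Protocol 8.1.1) uses 37% against 22% at two-sided 0.025. With about 433 and 217 children, an unstratified normal approximation gives 95.8%. With 490 Moderate children split 327 to 163, it gives 88.2%. Both agree with the stated more than 90% and more than 80%. This point does not dispute them; they supply the planning rates used below.

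**2. Which factors are in the imputation model.**

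| Factor in SAP 6.6 | vIGA-AD endpoints | EASI-75 |
|---|---|---|
| Actual baseline vIGA-AD | main effect | main effect |
| Randomized vIGA-AD | nearly, through the actual score | nearly, through the actual score |
| Baseline EASI (two groupings) | absent | main effect, as the score |
| Sex, race, ethnicity, BSA (two groupings), skin type, prior-steroid response, facial involvement | absent | absent |
| Treatment by any factor | absent | absent |

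Baseline vIGA-AD is counted as a predictor for the vIGA-AD endpoints for two reasons. Step 1 names it among the scores, and step 2 words its inclusion for other scales as an addition to what is already there.

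**3. Rough bound.** Suppose a share m of a level's outcomes is imputed with the overall effect D_all instead of the level's own effect D_g. The expected estimate is (1 − m) × D_g + m × D_all, so the shift is m × (D_all − D_g). Take D_all = 15 points, as planned, and levels 10 points either side (assumed):

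| m (assumed) | True 5 points | True 25 points | Shift |
|---|---|---|---|
| 5% | 0.95 × 5 + 0.05 × 15 = 5.5 | 0.95 × 25 + 0.05 × 15 = 24.5 | 0.5 |
| 10% | 6.0 | 24.0 | 1.0 |
| 15% | 6.5 | 23.5 | 1.5 |

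**4. Simulation of step 2.** Both simulations use 650 children, 2:1 allocation, five-level scores and random monotone dropout. Effects and dropout are assumed.

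- *Quarter-size subgroup with no effect, 28 points elsewhere.* The overall effect is 0.25 × 0 + 0.75 × 28 = 21 points. At about 5%, 10% and 15% missing, the subgroup difference is biased by +0.8, +1.6 and +2.3 points. The bound (m × 21) is 1.05, 2.1 and 3.15. With the factor and its interaction in the model, the bias is 0.0, −0.1 and −0.1.
- *Two half-size levels with true differences near 5 and 34 points.* For a factor outside the model, the gap between levels shrinks by 4–5%, 7–10% and 12–14% at 5%, 10% and 15% missing, depending on when children drop out. For baseline vIGA-AD as the subgroup factor (main effect present, interaction absent), the gap shrinks by about 2–3%, 4–6% and 6–9%. With the factor and its interaction added for the outside factor, shrinkage at 10% missing is about 0–2% (Monte Carlo standard error about 0.7 percentage points).

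**5. Scale.** A subgroup holding 25% of 650 has about 108 active and 54 vehicle children. At the planning rates the standard error is √(0.37 × 0.63/108 + 0.22 × 0.78/54) = √(0.00216 + 0.00318) = 0.073, or about 7 points. A shift of 0.5 to 1.5 points is therefore about 0.07 to 0.2 standard errors.

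**The case against.** The strongest reply is that the effect is minor and easily overstated. Four stronger readings are tempting, and the documents do not support them.

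- *The model contains no subgroup variable.* Actual baseline vIGA-AD is both a predictor and a listed factor, and randomized vIGA-AD nearly duplicates it. Baseline EASI is a predictor for EASI-75. For these factors only the interaction is missing.
- *Each missing child is given the overall treatment effect.* Children who stop for an adverse event or lack of efficacy are set to non-success. Others are imputed from their own Week 1 and Week 2 scores where observed, which carry some subgroup information. Early-termination data falling in the Day 23 to 43 window (SAP 5.4) count as Week 4. Step 1 names no treatment term, so it passes on no treatment effect directly.
- *Every subgroup estimate is pulled, and always toward consistency.* The pull needs imputed values and truly different effects. Its direction is established here only for monotone dropout at random; dropout that depends on unseen outcomes could bias either way.
- *A subgroup with no benefit will appear to benefit.* Even the deliberately large contrast in step 4 adds only 0.8 to 2.3 points. Rescaled from a 21-point to the planned 15-point overall effect (× 15/21), that is about 0.6 to 1.6 points.

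It is also fair to say that no planned decision rests on these displays: the testing sequence in SAP 6.5 does not include them, and SAP 12.4 specifies no interaction test. The Moderate-at-randomization secondary endpoint uses the same model, but it is specified in SAP 6.2.1 and 12.2. In the second simulation its estimate moved by at most 0.7 points at 15% missing, with an assumed gap near 29 points between Mild and Moderate.

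These replies limit the size and reach of the point. They do not remove it: the model still lacks every interaction and most of the factors, and SAP 12.4 supplies nothing in their place.

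**Conclusion.** The point holds as a minor refinement. SAP 12.4 estimates effects by subgroup from imputations that carry no treatment-by-subgroup term and omit most of the factors. Given truly different effects and dropout at random, the expected result is a pull toward the overall effect. It is roughly bounded by the imputed share times the distance between the subgroup and overall effects.

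The size rests on assumed missingness and assumed differences between subgroups, since the documents state neither. Under those assumptions the pull is well inside the sampling error of a subgroup estimate. It concerns how the subgroup forest plots are read and gives no reason to doubt the primary or secondary tests.

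**What to change.** Add to SAP 12.4:

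> For each subgroup factor, step 2 of Section 6.2.1 will be rerun with the factor (unless it is already a predictor) and its interaction with treatment as additional independent variables. That factor's subgroup estimates will be taken from those runs. Levels with too few subjects in either arm (minimum to be stated before unblinding) will be pooled for the imputation only. For non-monotone gaps, step 1 will be run by treatment arm, with the factor included where numbers allow. Observed-data subgroup results will be shown beside the multiple imputation forest plots. The primary and secondary analyses keep the current imputations.

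Three details matter:

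- Adding actual baseline vIGA-AD a second time would be collinear, hence the exception for existing predictors.
- The existing cut-off in SAP 12.4 is fewer than 10 children across both arms. A level of 12 would pass it with only about 4 vehicle children at 2:1, too few to support an interaction, so the pooling rule should apply per arm.
- The observed-data results set adverse-event and lack-of-efficacy discontinuations to missing (SAP 5.5). They serve as a comparison, not a replacement.

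The cost is SAP wording, one extra imputation run for each of the 12 factors, and slightly larger variance of the subgroup estimates. ITT totals from a factor-specific run may also differ slightly from the primary result, which a footnote can state.

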12.5 Summary of Primary and Secondary Efficacy Analysis

Table 5 provides a summary of the primary and sensitivity analyses that will be provided for primary and secondary efficacy endpoints.

Table 5 Summary of Primary and Secondary Efficacy Analyses

Efficacy Endpoint	Primary Analysis	Sensitivity Analysis
Primary (refer to Section 12.1)		
vIGA-AD Success (a score of '0' or '1' plus at least a 2-grade improvement) at week 4	ITT, multiple imputation (CMH)	#1 ITT, Tipping point (CMH)) #2 ITT, non-responder imputation (CMH) #3 ITT, observed data (CMH) #4 PP, observed data (CMH)
Secondary (refer to Section 12.2)		
vIGA-AD Success (a score of '0' or '1' plus at least a 2-grade improvement) at week 4	vIGA-AD Moderate ITT, multiple imputation (chi- square)	#1 vIGA-AD Moderate ITT, non- responder imputation (chi-square) #2 vIGA-AD Moderate ITT, observed data (chi-square)
-EASI-75 at week 4 -vIGA-AD score of '0' or '1' at week 4 -vIGA-AD Success at week 2 -vIGA-AD score of '0' or '1' at week 2 -vIGA-AD Success at week 1 -vIGA-AD score of '0' or '1' at week 1	ITT, multiple imputation (CMH)	#1 ITT, non-responder imputation (CMH) #2 ITT, observed data (CMH)

 Innovaderm Research	STATISTICAL ANALYSIS PLAN, Version 1.0
Protocol Number: ARQ-151-315	Sponsor: Arcutis Biotherapeutics, Inc.

13 SAFETY ANALYSIS

Safety analyses will be conducted using the safety population. Subjects will be analyzed based on the treatment received and the stratum they belong to.

No formal inferential statistics will be performed on safety assessments.

13.1 Adverse Events

Adverse events (AEs) will be coded according to the latest available version of Medical Dictionary for Regulatory Activities (MedDRA) (Version 25.0).

Treatment emergent adverse events (TEAEs) are defined as any AEs with onset on or after the first study drug application. See [Appendix 2](#) for handling of completely or partially missing dates for AEs. In the case where it is not possible to define an AE as treatment emergent or not, the AE will be classified as treatment emergent. All reported TEAEs will be summarized by treatment group.

Overall summary will be presented, which will include the total number of events, and the number and percentage of subjects who experienced TEAE, TEAE by the strongest relationship, TEAE by the maximum severity, treatment-related TEAE by maximum severity, treatment-emergent serious AE (TESAE), treatment-emergent Non-SAE, TEAE leading to study treatment discontinuation, TEAE leading to study discontinuation, TEAE on an application site, and TEAE leading to death.

The number and percentage of subjects who experience TEAE will be summarized by SOC and PT within SOC. Unless otherwise specified, a subject experiencing the same TEAE multiple times will be counted only once for the corresponding PT. Similarly, if a subject experiences multiple TEAEs within the same SOC, the subject will be counted only once for that SOC. TEAEs will be sorted alphabetically by SOC and within each SOC the PT will be presented by descending frequency in the safety analysis set. A treatment-related TEAE is defined as any TEAE that is assessed by the Investigator as likely, probably, or possibly related to study treatment. TEAE that is assessed as unrelated or unlikely will be defined as not treatment-related. If a subject experiences more than one TEAE within different relationship categories within the same SOC/PT, only the worst case (the strongest relationship) will be reported. TEAE with an unknown relationship will be considered as treatment-related.

The number and percentage of subjects who experience TEAE will be summarized by SOC, PT and the maximum severity (mild/moderate/severe/life threatening/death related to AE). If a subject experiences more than one TEAE within different severity categories within the same SOC/PT, only the worst case (the maximum severity) will be reported. TEAE with an unknown severity will be considered as severe.

 Innovaderm Research ■■■	STATISTICAL ANALYSIS PLAN, Version 1.0
Protocol Number: ARQ-151-315	Sponsor: Arcutis Biotherapeutics, Inc.

The number and percentage of subjects who had TESAE, TEAE leading to discontinuation of study drug, treatment-emergent Non-SAE, will be summarized by SOC and PT within SOC.

Frequency and percentage of subjects who experience TEAE on an application site will be summarized by SOC and PT.

A table and plot of most frequent TEAE (' $\geq 1\%$ ') by PT will be provided by treatment arms (overall TEAE, overall TESAE will be included in the same plot).

All the AEs will be listed. Any TEAE leading to death will also be included in the AE listing (if there is any). The TEAE related to application site will be flagged in the AE listing.

13.2 Clinical Laboratory

Descriptive statistics for the observed values in chemistry and hematology, change from baseline and percent change from baseline values will be presented by treatment group at each scheduled visit.

Shift tables from baseline to each post-baseline assessments describing shifts to out-of-normal range will be provided for chemistry and hematology. Only subjects with a baseline result and a result at the specified visit for the parameter will be considered.

Listings of abnormal laboratory will be provided for each parameter where a subject had at least one abnormal result.

Laboratory data will be presented in SI units.

13.3 Vital Signs

Descriptive statistics will be presented for vital signs (systolic blood pressure, diastolic blood pressure, heart rate, body temperature, and weight). Observed values, change from baseline and percent change from baseline values will be presented by treatment group at each scheduled visit.

The number and percentage of subjects with gain or lose $\geq 5\%$ from baseline in body weight over the course of the study will be summarized. The BMI percentile rather than BMI kg/m^2 will be summarized using descriptive statistics (n, mean, standard deviation, median, Q1, Q3, minimum, and maximum) on observed values, change from baseline and percent change from baseline values.

A listing of all vital sign assessments including weight, BMI, and BMI percentile will be provided.

 Innovaderm Research ■■■	STATISTICAL ANALYSIS PLAN, Version 1.0
Protocol Number: ARQ-151-315	Sponsor: Arcutis Biotherapeutics, Inc.

13.4 Local Tolerability Assessments

The investigator's assessment of the application site reaction will be summarized by visit using both categorical methods (number and percentage of subject with each score) as well as continuous methods (e.g., mean, standard deviation, etc.)

Local tolerability (burning/stinging sensation) assessed by the parent/caregiver for the subject will be summarized using number and percentage similarly.

13.5 Physical Examination

The number and percentage of subjects with normal and abnormal findings in the physical examination will be presented by body system and treatment group at each study visit.

14 PHARMACOKINETICS ANALYSIS

PK data will be included in SDTM/ADaM datasets. A PK report will be provided by the study Pharmacokineticist.

 Innovaderm Research	STATISTICAL ANALYSIS PLAN, Version 1.0
Protocol Number: ARQ-151-315	Sponsor: Arcutis Biotherapeutics, Inc.

